## 5.4.3 Vaccination doses:

# Part 1:

For each vaccine, 300 mcg of each of the long peptides in LPV7 and 200 mcg of the tetanus helper peptide will be administered, plus 1 ml IFA or the dose of TLR agonists as specified in Table 1A and section 5.2.1.

#### Part 2:

For each vaccine, 300 mcg of each of the long peptides in LPV7 will be administered, plus 1 ml IFA and the dose of TLR agonists as specified in Table 1B and Section 5.2.1.

#### 5.4.4 Route of administration:

At each injection site for emulsions with IFA, a single needle puncture is to be performed, with delivery of 1 cc volume into the subcutaneous tissue and 1 cc volume into the dermis. This usually will require advancing the needle into the subcutaneous tissue to deliver the first 1 cc over an area within reach of that needle, then pulling the needle back to near the skin puncture site, and advancing it into the intradermal tissue for delivery of the remaining 1 cc. For injections with peptides in polyICLC without IFA, the total volume will be 1 ml, which will be divided between subcutaneous tissue and dermis as above.

#### 5.4.5 Post-Vaccination Observation

All participants will be closely observed for adverse events for at least 20 minutes following each vaccination. Any time thereafter, participants should report any adverse events to the research coordinator or research clinician.

## 5.4.6 Biopsies of Vaccine site and normal skin:

Each participant in Part 1 and Part 2 will undergo biopsy of the vaccine site at two time points (days 8 and 22; one week after vaccines 1 and 3). Control biopsies of clinically normal skin (three 4-mm punch biopsies of the dermis and subcutaneous tissue) will be taken at the same time points (days 8 and 22), for the first 6 participants enrolled in Part 1.

The biopsies will consist of three 4-mm punch biopsies of skin. Note that vaccine sites will be rotated to different skin sites for each vaccination; so there will not be repeat injection of vaccines into the prior skin biopsy sites.

Version Date: 07-31-17

- 5.4.6.1 The punch biopsies of normal skin will be taken from an upper thigh or upper arm, and will be preserved/processed as follows:
  - 5.4.6.1.1 Normal 1: quick-frozen in liquid nitrogen.
  - 5.4.6.1.2 Normal 2: preserved in formalin, then paraffin-embedded
  - 5.4.6.1.3 Normal 3: preserved in RNA later.
- 5.4.6.2 The punch biopsy specimens of the VSME will be preserved/processed as follows:
  - 5.4.6.2.1VSME sample 1: quick-frozen in liquid nitrogen.
  - 5.4.6.2.2VSME sample 2: preserved in formalin, then paraffin-embedded
  - 5.4.6.2.3 V SME sample 3: preserved in RNA later.
- 5.4.6.3 Their evaluation is summarized in the Study Manual.
- 5.4.6.4 The specimens should be put into liquid nitrogen, formalin, or RNA later within 15 minutes if at all possible, and ideally within 5 min of excision. Delays beyond 15 minutes should be documented. This information should be documented on the Skin Biopsy Submission Form.

### 5.5 Modification/Discontinuation of Treatment

## 5.5.1 Dose Modifications

There will be no dose modifications of the vaccine components.

### 5.5.2 Discontinuation

If participants are discontinued prior to one or more scheduled skin biopsies, they will not receive those biopsies. Protocol treatment will be discontinued for any of the following reasons:

- 5.5.2.1 Any dose-limiting toxicity as defined in Section 7.4.
- 5.5.2.2 In circumstances where assessment of an AE is limited, such as by intercurrent illness, or when laboratory studies are required to assess for other causes of toxicity, the vaccine/biopsy schedule may be interrupted for up to 7 days. Delay of one vaccine administration, biopsy, or evaluation visit by up to 7 days will not be considered a protocol violation, regardless of attribution. If more than one vaccine is delayed by 8 days or more, treatment must be discontinued.
- 5.5.2.3 Disease progression requiring other therapy (e.g. surgery under general anesthesia, radiation, chemotherapy, or steroid therapy). The appearance of small metastases or recurrent tumor deposits will not be a basis for discontinuing the vaccinations. Biopsy to determine the nature of new lesions, or minor surgical procedures to excise a new lesion, will not be a basis for discontinuing vaccinations.

- 5.5.2.4 Initiation of cytotoxic chemotherapy, radiation therapy, steroid therapy as detailed under Section 4.2.5, or other immunosuppressive therapy.
- 5.5.2.5 Any other potential adverse reaction deemed sufficiently serious to warrant discontinuation of therapy by the Principal Investigator or one of the sub-investigators.
- 5.5.2.6 Noncompliance with the requirements of the study.
- 5.5.2.7 Therapy may be discontinued at the participant's request.
- 5.5.2.8 Therapy may be discontinued at the discretion of an investigator.
- 5.5.2.9 Pregnancy. Pregnant participants will continue to be followed for the duration of the pregnancy.

#### 5.5.3 日ective Withdraw al

A participant who is enrolled but neither receives any study drug nor has a skin biopsy on protocol may be replaced. Every attempt will be made to evaluate any data from these participants for endpoint assessment.

# 5.5.4 Delayed Visit for Reasons Other Than Toxicity

A schedule for return visits should be established at the first visit. If a participant misses a treatment, the missed treatment will be administered as soon as possible, so that the subsequent vaccinations are given in the appropriate intervals. Treatment may be continued for an additional time period, if needed. Participants who are vaccinated outside of the established schedule should return to the original schedule as soon as possible.

The table below defines what constitutes a delayed visit, whether the participant should continue to be treated, and whether a protocol violation/deviation should be reported and recorded. The range of days is counted from the original scheduled date.

Table 6. Delayed Visit for Reasons other than Toxicity				
Treatment Period	Range of Days	Participant Treatment	Protocol Deviation	
Vaccine 1				
Day 1	± 2 days	Vaccine/Labs	No	
	± 3 to 7 days	Vaccine/Labs	Yes	
	± 8 or more days	Labs	Yes	
Vaccine 2/Biopsy*				
Day 8	± 2 days	Vaccine/Labs/Biopsy	No	
	± 3 to 7 days	Vaccine/Labs/Biopsy	Yes	
	± 8 or more days	Labs	Yes	
Vaccine 3*				
Day 15	± 2 days	Vaccine/Labs	No	
	± 3 to 7 days	Vaccine/Labs	Yes	

	± 8 or more days	Labs	Yes
Assessment/Biopsy			
Day 22	± 2 days	Biopsy/Labs	No
	± 3 to 7 days	Biopsy/Labs	Yes
	± 8 or more days	Labs	Yes
Assessment			
Day 43	L O dovo	Labs	No
	± 2 days	1 1 1	
	± 3 to 7 days	Labs	Yes
	± 8 or more days	Labs	Yes
Vaccines 4-6*			
Days 36, 57, 78	± 7 days	Vaccine/Labs	No
	± 8 to 14 days	Vaccine/Labs	Yes
	± 15 or more days	Labs	Yes
Assessment			
Day 85 (Week 12)	± 7 days	Labs/Scans	No
	± 8 to 14 days	Labs/Scans	Yes
	± 15 or more days	Labs	Yes
Follow-up			
Week 26, Year 1 and 2	± 7 days	Scans/Labs	No
	± 8 to 30 days	Scans/Labs	Yes

A participant will be taken off protocol treatment if more than one vaccination is delayed [ $\pm$  3 to 7 days] during the treatment period.

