Regimen: Patients will be registered on this phase I/II trial and will be vaccinated with LPV7 at 300 mcg peptide/dose every week x 3 then every 3 weeks x 3.

For Part 1, the adjuvants are described, and will be administered to patients in 7 study groups as shown in Table 1A. This incorporates an adaptive design with sequential initiation of accrual to study Zones with increasing numbers of adjuvants (Arms A-C, then D-F, then G). Details are in Section 9.0 and Appendix 1 (X-page).

For Part 2, the adjuvants will be administered to patients in 1 study group as shown in Table 1B.

Vaccine site biopsies: In each patient, three 4-mm punch biopsies will be performed of the skin at vaccine sites at two time points: 1 week after vaccine #1 (day 8) and one week after vaccine #3 (day 22). As negative controls, 3 punch biopsies will be obtained of clinically normal skin (not at the vaccine site) in the first 6 patients in Part 1 at the same time points (days 8 and 22). Details are provided in section 5.4.6.2.

Leadership: This trial will be performed at two institutions in patients with high-risk resected stage IIB-IV melanoma. The lead institution for this trial will be the University of Virginia, and the PI will be [name]. The institutional PI at M.D. Anderson Cancer Center will be [name]. Part 2 will be conducted at the University of Virginia only.

Population: Criteria for inclusion include:

- age 18 years or older
- expression of HLA-A1, -A2, -A3, -B35, or -B51
- histologically or cytologically proven Stage IIB-IV melanoma rendered clinically free of disease by surgery, other therapy, or spontaneous remission. Small (<1cm) findings that are equivocal on radiologic or clinical imaging will not be a basis for exclusion.
- ECOG performance status 0-1 (Appendix 3)
- Adequate hepatic and renal function
- Weight at least 50 kg (110 lbs)

NOTE: Patients will be excluded if they are pregnant or are immunosuppressed, or have previously received vaccines containing an incomplete Freund's adjuvant.

Accrual: For Part 1, the maximum accrual to the study is estimated from the simulations to be approximately 52 patients. Adjusting for 10% ineligibility/dropout/withdrawal rate, maximum total target accrual is estimated at 58 patients. For Part 2, target accrual is estimated to be 16 eligible patients. Adjusting for 10% ineligibility/dropout/withdrawal rate, maximum total accrual for part 2 is estimated at 18 patients.

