# 6.2 Treatment

The following evaluations will be performed on an outpatient basis on each of the listed days. Blood for these evaluations should be obtained prior to the vaccine injection if a vaccine is scheduled to be administered. Results of those tests are not required prior to administering the vaccine on that date.

## 6.2.1 Day 1

- Interval history and physical examination directed at new signs and symptoms.
- Vital signs
- Weight
- Performance status
- Visual acuity exam using a Snellen chart, and color vision exam using an Ishihara eye chart
- Neurologic function, general.
- Note hair and eve color
- Assessment of skin for vitiligo
- Anti-nuclear antibody and rheumatoid factor (4 ml total)
- Baseline symptoms, codable in the NIH CTCAE v.4.03, to be recorded as preexisting conditions unrelated to the research protocol interventions
- Distribute participant toxicity diary
- Medication review
- Blood collection for immunologic testing: The following blood samples for research will be provided to UVA and processed by the UVA BTRF and stored by the UVA-HITC IML:
  - 120 cc blood collected in heparinized green top tubes for lymphocytes. This may be decreased to 100 cc if more blood must be drawn for safety or screening labs, in order to comply with institutional limits on total blood drawn in a day.
  - 20 cc blood collected in red top tubes for serum.
- Vaccine administration

# 6.2.2 Day 8

 Interval history and physical examination directed at new signs and symptoms. Examination of the vaccine site(s) should be included..

Version Date: 07-31-17

- Vital signs
- Weight
- Performance status
- Review of adverse events
- Review of participant toxicity diary and distribute new toxicity diary
- Medication review
- Blood collection for immunologic testing:\_The following blood samples for research will be provided to UVA and processed by the UVA BTRF and stored by the UVA-HITC IML:
  - 80 cc blood collected in heparinized green top tubes for lymphocytes.
  - 20 cc blood collected in red top tubes for serum
- Biopsies of 1st vaccine site (all patients), and biopsies of normal skin (patients 1-6 only in Part 1). Details in section 5.4.6 and in Study Manual.
- Vaccine administration

## 6.2.3 Day 15

- Interval history and physical examination directed at new signs and symptoms. Examination of the vaccine site(s) should be included.
- Vital signs
- Weight
- Performance status
- Review of adverse events

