# 9.7.2 Immunologic response:

Subjects are evaluable for immune response if at least one post treatment sample is measurable for response. Peak immunogenicity will be evaluated by direct Elspot assay against the defined nonamer peptides in the peripheral blood. The presence or absence of an immune response will be defined by induction of at least a 2-fold increase in IFN-gamma-secreting cells over background, and over pre-existing responses, and at least 30 IFN-gamma secreting spots per 100,000 CD8 T cells, as described . This assessment will be performed on blood through week 12, although a minimum of 4 weeks of data will be used to guide decisions about the range of optimal dose combinations. IRR is defined as the proportion of participants where presence (as defined above) of an immune response has been observed.

Durable immunogenicity will be evaluated week 26 by Ellspot assay against the defined nonamer peptides in the peripheral blood. The presence or absence of an immune response at that time will be defined by induction of at least a 2-fold increase in IFN-gamma-secreting cells over background, and over pre-existing responses, and at least 30 IFN-gamma secreting spots per 100,000 CD8 T cells, as described . This assessment will be performed on blood through week 26.

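### Table 6 ties the day 43 and day 85 immunology draws to the original calendar while vaccines 4 to 6 may move by 7 days, so a draw can follow its vaccine by 0 to 2 days without a deviation

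*Combined protocol and SAP*

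**What the plan says.** Section 5.5.4 anchors every window in Table 6 to the calendar: "The range of days is counted from the original scheduled date". It adds: "Participants who are vaccinated outside of the established schedule should return to the original schedule as soon as possible". The row for vaccines 4 to 6 reads "Days 36, 57, 78 ± 7 days Vaccine/Labs No", and the last on-study assessment reads "Day 85 (Week 12) ± 7 days Labs/Scans No". The first line of the day 43 row is poorly legible; I read it as ±2 days, which fits the deviation row of 3 to 7 days below it.

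Appendix 1 and section 6.2 place vaccines on days 1, 8, 15, 36, 57 and 78. Immunology blood is drawn on days 1, 8, 22, 43 and 85, and then at week 26 and later. No immunology blood is drawn on day 57 or 78. For days with both blood and vaccine, section 6.2 fixes the order: "Blood for these evaluations should be obtained prior to the vaccine injection if a vaccine is scheduled to be administered".

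For peak response, section 9.7.2 states: "This assessment will be performed on blood through week 12". One measurable post-treatment sample makes a participant evaluable, and no interval from the preceding vaccine is required. The Protocol Precis times the vaccine-site biopsies relative to vaccination: "1 week after vaccine #1 (day 8) and one week after vaccine #3 (day 22"). Blood draws carry no such wording.

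**The concern.** The calendar puts the day 43 and day 85 draws 7 days after vaccines 4 and 6. Table 6 lets the vaccine move and leaves the draw where it was. A site that follows the table exactly can draw blood too soon after a vaccine to reflect it, or on the same day before the injection. For vaccine 4 the table can go further and classify the well-timed sample as the deviation.

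Objective 5 concerns the immunogenicity of all six same-site vaccines, and it rests on peak ELIspot response through week 12. Day 85 is the only sample in that period placed after vaccines 5 and 6. If it comes on or before the day of vaccine 6, no sample in the peak window reflects the full regimen. Section 9.5.2 then judges 16 participants against a fixed count of 12 responders, so each participant is worth 1/16 = 6.25 percentage points.

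**Working it through.** **The plan's own figure.** The exact (Clopper-Pearson) lower one-sided 80% limit for 12/16 is the 20th percentile of Beta(12, 5) = 61.55%. Section 9.5.2 gives 61.5%, so it reproduces.

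**Gap formula.** Gap = (scheduled draw day + draw shift) - (scheduled vaccine day + vaccine shift). The calendar gaps are 43 - 36 = 7 and 85 - 78 = 7 days. Within the windows that carry no deviation:

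| Pair | Vaccine days | Draw days | Smallest gap | Largest gap |
|---|---|---|---|---|
| Vaccine 4, day 43 | 29 to 43 | 41 to 45 | 41 - 43 = -2 | 45 - 29 = +16 |
| Vaccine 6, day 85 | 71 to 85 | 78 to 92 | 78 - 85 = -7 | 92 - 71 = +21 |

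Because blood is taken first, a gap of 0 is a pre-vaccine sample.

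**Day 43.** If vaccine 4 is d days late, the latest compliant draw is 45 - (36 + d) = 9 - d days after it. A 7-day gap is therefore available only for d of 2 or less. At d = 7 (vaccine on day 43, no deviation) the limit is 2 days, and a draw 7 days after the vaccine falls on day 50, which is a deviation.

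**Day 85.** Here the ±7-day window always permits a 7-day gap: vaccine 6 on day 85 allows a draw on day 92. It does not require one. Vaccine 6 on time on day 78 with a draw on day 78 gives a gap of 0. If vaccine shifts are limited to 2 days, the day 43 gap stays at 3 to 11 days, but the day 85 gap still runs from -2 to +16.

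**Permitted day pairs (not probabilities).** For day 85 there are 15 × 15 = 225 pairs. In 28 the draw precedes the vaccine, in 8 they share a day, and in 55 the gap is 2 days or less. With visits kept in order, 225 - 28 = 197 pairs remain. Of these, 8 (4%) have a gap of 0 and 55 - 28 = 27 (14%) have a gap of 0 to 2 days. For day 43, 3 of 75 pairs are reversed and 3 share a day.

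**Biopsy.** With no deviation, vaccine 3 falls on days 13 to 17 and the biopsy on days 20 to 24, a gap of 3 to 11 days. Vaccine 3 is still given when 3 to 7 days late (a deviation), which can put it on day 22 itself.

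**Effect on the Part 2 rule.** One lost responder turns 12/16 into 11/16, and the lower limit drops from 61.5% to 55.1%. Suppose the true response rate is 75% and a fraction f of responders is missed; both are assumptions. The probability of at least 12/16 is then:

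| f | Detected rate | P(at least 12/16) |
|---|---|---|
| 0 | 75% | 63.0% |
| 5% | 71.25% | 49.4% |
| 10% | 67.5% | 36.6% |
| 20% | 60% | 16.7% |

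**The case against.** A reader might infer that the peak response is missed. The documents do not support that. Days 8, 22, 43 and 85 all count, so a participant is misclassified only if the response had not appeared earlier and the later draw is also badly timed. Nothing in the documents gives that joint frequency.

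A reader might also take 36/225 = 16% as the share of day 85 draws on or before the day of vaccine 6. That figure treats the two visits as independent, and 28 of the 36 pairs need the visits out of order, against the sequence in section 6.2 and Appendix 1.

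Other points have weight:

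- The one-week wording applies to the biopsies; for blood the 7-day gap is inferred from the calendar.
- The line under Table 6 takes a participant off treatment after more than one delay of 3 to 7 days, which limits repeated slips.
- Section 5.5.4 also asks that later vaccinations keep appropriate intervals.
- The documents show no separate visit table for Part 1, so no bias between Arms E and E2 is demonstrated.
- The Study Manual is not available and could hold a sampling rule.

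What stands is narrower. A single slip is enough, and for day 85 none is needed. Keeping visits in order still leaves gaps of 0 to 2 days. For vaccine 4 the rule makes the 7-day sample non-compliant once the vaccine is more than 2 days late. That is a stated rule that favors the wrong sample, not a missing detail.

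**Conclusion.** The concern holds in limited form, and the table should be changed. The compliant vaccine-to-draw gap runs from -2 to +16 days at day 43 and from -7 to +21 days at day 85, against 7 on the calendar. Only the gaps of 0 or more are realistic if visits stay in order. Day 43 shows the clearer fault in the rule, because a late vaccine 4 excludes the 7-day sample. Day 85 carries the greater consequence, because no later sample enters the 12-week peak.

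The supportable consequence is that a response may be missed or understated if it had not already appeared on day 8, 22 or 43. Its frequency is unknown. The 6.25-point step and the fall from 61.5% to 55.1% show what one lost responder would cost, not what is expected. The verdict rests on reading the day 43 window as ±2 days and on there being no sampling rule in the Study Manual that overrides Table 6.

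**What to change.** In Table 6, for Part 2, count the day 43 draw from the actual date of vaccine 4, the day 85 draw from that of vaccine 6, and the day 22 biopsy from that of vaccine 3. Set a target of 7 days, always after that vaccine. Keep the existing widths (±2, ±7 and ±2 days) and leave the vaccine windows unchanged. The day 43 draw and the biopsy then fall 5 to 9 days after their vaccine, and the day 85 draw 1 to 14 days after.

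Keep the week 12 cut-off in section 9.7.2, so that the endpoint still matches Part 1. Add two statements: the Day 85 (Week 12) visit sample counts even if re-anchoring moves it later, and samples from participants who stop early still count. List the actual vaccine-to-draw interval for each participant in Arms E and E2.

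The cost is wording, with no extra visits or samples. Some draws move later: with vaccines inside their windows, the latest are day 43 + 9 = day 52 and day 85 + 14 = day 99. Part 1 was sampled under the old rule, which is why the listing should cover Arm E. Short gaps at day 85 remain possible within ±7 days, and the listing will show them.

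Separately, three passages conflict and must be reconciled. Table 6 records no deviation for vaccines 4 to 6 within 7 days. The line beneath it ends treatment after more than one delay of 3 to 7 days. Section 5.5.2.2 ends treatment when more than one vaccine is delayed by 8 days or more.

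### Read literally, the note under Table 6 ends treatment for two doses among vaccines 4-6 that the table itself counts as on time

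*Combined protocol and SAP*

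**What the plan says.** Section 5.5.4 presents Table 6 as the rule for what counts as a delayed visit, whether treatment continues and whether a deviation is recorded. "The range of days is counted from the original scheduled date".

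- **Vaccines 1-3 (days 1, 8, 15):** up to 2 days off, vaccine given, no deviation; 3 to 7 days off, vaccine given, deviation; 8 days or more, labs only.
- **Vaccines 4-6 (days 36, 57, 78):** up to 7 days off, vaccine given, no deviation; 8 to 14 days off, vaccine given, deviation; 15 days or more, labs only.

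The note below the table reads "A participant will be taken off protocol treatment if more than one vaccination is delayed", followed by a bracketed range ending "3 to 7 days] during the treatment period". It names no vaccine numbers. The headings for vaccine 2, vaccine 3 and vaccines 4-6 carry an asterisk.

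Section 5.5.2.2 opens with interruptions to assess an adverse event, where "the vaccine/biopsy schedule may be interrupted for up to 7 days". It closes with a second rule on repeated delays: "If more than one vaccine is delayed by 8 days or more, treatment must be discontinued". That sentence gives no cause.

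Section 9.7.2 sets evaluability: "Subjects are evaluable for immune response if at least one post treatment sample is measurable for response".

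**The concern.** The note counts delays of 3 to 7 days at any vaccine. For vaccines 4-6 that range lies wholly inside the window the table treats as on schedule. A participant can therefore have no recorded deviation and still meet a rule that ends treatment.

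Part 2 uses this table. It asks what six vaccines at one skin site do, in 16 eligible participants. A participant stopped over two such doses may receive only four or five vaccines and remains in the denominator of the immune response rate, because one measurable post-treatment sample is enough. Section 5.5.3 does not help: it allows replacement only of someone who had neither study drug nor a skin biopsy. Whether a participant completes the regimen should not turn on two doses the schedule accepts.

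**Working it through.** **Step 1. Two late doses among vaccines 4-6, each 5 days late (non-toxicity reason).** Take vaccine 4 on day 36 + 5 = 41 and vaccine 5 on day 57 + 5 = 62.

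- Table 6: both doses are within 7 days, so both are given and neither is a deviation.
- Section 5.5.2.2: neither delay reaches 8 days, so its stop is not met.
- Note under Table 6: two vaccinations are delayed 3 to 7 days, so the participant comes off treatment.

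The note alone ends treatment. If vaccine 5 is withheld as the second late dose, vaccines 5 and 6 are lost, leaving 4 of 6. If vaccine 5 is given before the rule is applied, only vaccine 6 is lost.

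**Step 2. How far the literal note reaches.** Six vaccines form 15 pairs. For two delays of 3 to 7 days:

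- 3 pairs lie within vaccines 1-3. The table records two deviations, and the note fits.
- 9 pairs take one dose from vaccines 1-3 and one from 4-6. The table records one deviation, and the note removes the participant.
- 3 pairs lie within vaccines 4-6. The table records no deviation, and the note still removes the participant. This is the case at issue.

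**Step 3. Probable intent.** Among the vaccine rows, 3 to 7 days is a tier only for vaccines 1-3, where it marks a deviation. That suggests the note was not written for in-window doses of vaccines 4-6. Its wording does not say so, however, and the asterisk on the vaccines 4-6 row points the other way.

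**Step 4. Size.** The plan gives no figure to reproduce and no delay rate. Assume each of vaccines 4-6 independently has probability q of being 3 to 7 days late for a non-toxicity reason. The chance of two or more is 3q²(1 − q) + q³ = 3q² − 2q³. The expected number removed is 16 times that.

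- q = 0.05: 0.0075 − 0.00025 = 0.00725; × 16 = 0.12
- q = 0.10: 0.0300 − 0.0020 = 0.0280; × 16 = 0.45
- q = 0.20: 0.1200 − 0.0160 = 0.1040; × 16 = 1.66

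These figures count only pairs within vaccines 4-6, not the mixed pairs of step 2.

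**The case against.** The best defence is that a table row handles one dose while the note is a cumulative rule, so both can be followed. On this view the note governs the early doses, 5.5.2.2 governs repeated delays of 8 days or more, and nothing is left uncovered. The asterisk is weak evidence, since the table text is visibly damaged and the note carries no asterisk in the copy available.

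Much of this stands. It is a sensible account of what was intended, and a per-dose row does not by itself contradict a cumulative stop. But the note does not contain the restriction that this account needs. A cumulative rule on delays should count doses that the table treats as late, and here it counts doses that the table treats as on time.

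A reader might infer more, and the documents do not support it:

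- **That two delays of 8 to 14 days go unchecked.** The note's range does not reach them, but the last sentence of 5.5.2.2 names no cause and on its plain wording stops treatment.
- **That the 8 to 14 day row conflicts with 5.5.2.2.** The row says what to do with a single dose; 5.5.2.2 acts on more than one.
- **That sites would apply the rule differently.** Part 2 runs at the University of Virginia only.
- **That one slip carried forward at 3-week intervals becomes several delays.** Section 5.5.4 does say that "the missed treatment will be administered as soon as possible, so that the subsequent vaccinations are given in the appropriate intervals", but also that "Participants who are vaccinated outside of the established schedule should return to the original schedule as soon as possible". The carry-forward case needs that second instruction to be set aside.

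**Conclusion.** Wrong as written; minor severity. Taken literally, the note ends treatment for two in-window doses among vaccines 4-6, at a shorter delay than the stop in 5.5.2.2, and can cost a participant up to two of the six same-site vaccines.

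The expected number affected is 0.12, 0.45 or 1.66 of 16, at assumed delay probabilities of 5%, 10% or 20% per vaccine, with delays independent and the note applied literally. If staff read the note as covering only vaccines 1-3, no one is removed for this reason. The documents do not show how stopping early would change the Part 2 response count, so no such effect is claimed.

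**What to change.** Reword the note only. Keep its opening, "A participant will be taken off protocol treatment if more than one vaccination is delayed", and replace the bracketed range and the words after it with: beyond its no-deviation window in Table 6 (more than 2 days for vaccines 1-3; more than 7 days for vaccines 4-6). For vaccines 4-6 this matches the 8-day threshold in 5.5.2.2.

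Leave the stop rule in 5.5.2.2 without a restriction on cause. If it were confined to adverse-event delays, a participant with one 8-day delay of that kind and one 8-day scheduling delay could meet neither rule.

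The cost is one sentence, with no new visits or data. Participants with repeated delays of up to 7 days among vaccines 4-6 stay on treatment, as do those with one such delay and one deviation among vaccines 1-3, so intervals between the later vaccines may vary slightly more. If the sponsor does intend the stricter limit for vaccines 4-6, the note should say so expressly and the table's window should be narrowed to match.
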